5.3. REPLACEMENT OF PATIENTS

Patients must be replaced if they are considered not evaluable for efficacy, i.e., if they are withdrawn from the study due to significant clinical deterioration of unknown reason, hypersensitivity reactions, patient refusal or unrelated AEs without any tumor assessment after the start of study treatment.

Patients withdrawn from the study due to toxicity without any tumor assessments after the start of study treatment will be considered as “treatment failures” and will not be replaced.

The number of patients replaced will be reflected in the overall number of patients included into the trial.

5.4. STUDY TERMINATION (CLINICAL CUTOFF)

The planned study termination (clinical cutoff) will be six months after the last treatment visit of the last evaluable patient included in the study, or nine months after the last patient is included, whichever occurs first.

All patients on active treatment at the date of study termination will be offered to continue to receive PM00104 treatment off-study according to the Investigator criteria.

5.5. SCREENING EVALUATION

During the pre-treatment period, and once the patient has signed the Informed Consent Form, the Investigator will confirm the patient’s eligibility for the study by conducting the following assessments ([Table 8](#)).

Additional information on the collection and processing of PGx samples may be found in [Appendix 1. Samples, Methodology and Techniques of the Pharmacogenomic Substudy](#).

Table 8. Screening assessments.

	ASSESSMENT	TIME
1. History and clinical examination	♦ Written informed consent.	Prior to any specific study procedures (within four weeks prior to Day 1 of Cycle 1).
	♦ Medical history: 
○ Date of diagnosis of the primary disease.○ Demographic information (race/ethnicity, age).○ Prior treatments (surgery, radiotherapy, chemotherapy, immunotherapy), specifying the best response and the date of PD. ♦ Concomitant diseases and treatments.	Within four weeks prior to Day 1 of Cycle 1. Complete physical examination, ECOG PS and vital signs must be repeated on Day 1 of Cycle 1, prior to administration of the first PM00104 infusion.
	♦ Weight and height. ♦ Complete physical examination. ♦ Vital signs: heart rate, blood pressure and body temperature. ♦ Performance status (ECOG PS; see Appendix 2. ECOG Performance Status Assessment Scale).	Weight and height: repeat on Day 1 of Cycle 1 whenever clinically indicated.
♦ ECG. ♦ LVEF (ultrasound). All ECGs and LVEFs will be reviewed by an external cardiologist.	Within four weeks prior to Day 1 of Cycle. Repeat on Day 1 of Cycle 1 whenever clinically indicated.	

	ASSESSMENT	TIME
2. Laboratory tests	
 ◆ Hematology: differential WBC (neutrophils, lymphocytes), hemoglobin and platelets. ◆ Biochemistry A: liver function tests (ALT, AP, AST, LDH, total and direct bilirubin), creatinine, CPK, troponin I, glucose and serum electrolytes (Na⁺, Cl⁻, K⁺, Ca⁺⁺, Mg⁺⁺). ◆ Biochemistry B: total protein, albumin, amylase and lipase. CPK-MB fraction to be analyzed if CPK and/or troponin I are abnormal. In the case of grade ≥ 3 increase in serum cardiac troponin I, an ECG and cardiac ultrasound will be performed as soon as possible. 	
Within one week prior to Day 1 of Cycle 1.
 
Repeat on Day 1 of Cycle 1 prior to treatment with PM00104, if the treatment is administered more than one week after the screening test. Repeat Biochemistry B on Day 1 of Cycle 1 whenever clinically indicated.

3. Calculated creatinine clearance	Calculated using the Cockcroft and Gault formula (see Appendix 3. Cockcroft and Gault Formula).	
Within one week prior to Day 1 of Cycle 1.
 
Repeat on Day 1 of Cycle 1 prior to treatment with PM00104, if the treatment is administered more than one week after the screening test, or whenever clinically indicated.

4. Tumor assessment	CT-scan or MRI of all measurable/evaluable sites of disease, as per RECIST (see Appendix 4. Evaluation of Response. The RECIST).	
Within four weeks prior to Day 1 of Cycle 1.
 
Documentation of PD is mandatory.

5. Pregnancy test, if applicable		
Within two weeks prior to Day 1 of Cycle 1.
 
Repeat on Day 1 of Cycle 1 whenever clinically indicated.

6. PGx samples	See details in Appendix 1. Samples, Methodology and Techniques of the Pharmacogenomic Substudy .	
Tumor tissue samples obtained at disease diagnosis.
 
One blood sample taken prior to the first PM00104 infusion of Day1, Cycle 1.

7. Other tests	When indicated by the clinical and laboratory context.	Within four weeks prior to Day 1 of Cycle 1.

ALT, alanine aminotransferase; AP, alkaline phosphatase; AST, aspartate aminotransferase; CPK, creatine phosphokinase; CPK-MB, creatine phosphokinase-fraction MB; CT, computed tomography, ECG, electrocardiogram; ECOG, Eastern Cooperative Oncology Group; LDH, lactate dehydrogenase; LVEF, left ventricular ejection fraction; MRI, magnetic resonance imaging; PD, progressive disease; PGx, pharmacogenomics, PS, performance status; RECIST, Response Evaluation Criteria In Solid Tumors; WBC, white blood cells.

5.6. PATIENT REGISTRATION

After ensuring that the patient meets all eligibility criteria and has given written informed consent, she will be entered into the trial by contacting the clinical trial monitor designated by the Sponsor and faxing the completed Patient Registration Form (Fast Fact Sheet). The Sponsor will then check and confirm this Registration Form. A patient number will be provided to the site of enrolment within one working day. This patient number should be used on all future documentation and correspondence referred to this patient.

5.7. EVALUATIONS DURING TREATMENT

The following assessments will be done while the patient is on treatment ([Table 9](#)). A 2-day window is allowed for the different tests and procedures.

Table 9. Evaluations during treatment.

	ASSESSMENT	TIME
1. Clinical examination	
 ♦ Complete physical examination. ♦ Performance status (ECOG PS; see Appendix 2. ECOG Performance Status Assessment Scale). 	Day 1 of the first cycle prior to the PM00104 infusion, and then whenever clinically indicated.
	
 ♦ Vital signs: heart rate, blood pressure and body temperature. 	Before any PM00104 infusion.
	
 ♦ Weight and height. 	Repeat on Day 1 of each cycle prior to the PM00104 infusion, and then whenever clinically indicated.
	
 ♦ Intercurrent events, concomitant disease and treatments. 	Throughout the “on treatment” period (i.e., treatment plus 30 days following the last PM00104 administration).
2. Laboratory tests	
 ♦ Hematology: differential WBC (neutrophils, lymphocytes), hemoglobin and platelets. ♦ Biochemistry A: liver function tests (AP, ALT, AST, LDH, total and direct bilirubin), creatinine, CPK, troponin I, glucose and serum electrolytes (Na⁺, Cl⁻, K⁺, Ca⁺⁺, Mg⁺⁺). 	Repeat on Day 1 of each cycle prior to the PM00104 infusion, and then weekly. If NCI-CTCAE grade ≥ 3 occurs, the appropriate test(s) should be repeated at least every 2-3 days until recovery.
	
 ♦ Biochemistry B: total protein, albumin, amylase and lipase. CPK-MB fraction to be analyzed if CPK and/or troponin I are abnormal. In the case of grade ≥ 3 increase in serum cardiac troponin I, an ECG and cardiac ultrasound will be performed as soon as possible. 	Repeat on Day 1 of each cycle prior to the PM00104 infusion, and then whenever clinically indicated. If NCI-CTCAE grade ≥ 3 occurs, the appropriate test(s) should be repeated at least every 2-3 days until recovery.
3. Calculated creatinine clearance	Calculated using the Cockcroft and Gault formula (see Appendix 3. Cockcroft and Gault Formula).	Repeat on Day 1 of each cycle prior to the PM00104 infusion, and then whenever clinically indicated.
4. ECG	All ECGs will be reviewed by an external cardiologist.	Repeat on Day 1 of each cycle prior to the PM00104 infusion, and then whenever clinically indicated. In the case of grade ≥ 3 increase in serum cardiac troponin I, ECG will be performed as soon as possible.
5. LVEF	Cardiac ultrasound. All LVEFs will be reviewed by an external cardiologist.	Every other cycle, and then whenever clinically indicated. In the case of grade ≥ 3 increase in serum cardiac troponin I, cardiac ultrasound will be performed as soon as possible.
6. Tumor assessment	CT-scan or MRI of all measurable/evaluable sites, as per RECIST (see Appendix 4. Evaluation of Response. The RECIST).	Every other cycle (± one week) until PD.
7. Pregnancy test, if applicable		Whenever clinically indicated.
8. AEs	As per NCI-CTCAE, version 3.0.	Throughout the “on treatment” period.
9. PK	See Section 6 .	Only during the first two PM00104 infusions of the first cycle.
10. Other tests		When indicated, according to the clinical and laboratory context.

AE, adverse event; ALT, alanine aminotransferase; AP, alkaline phosphatase; AST, aspartate aminotransferase; CPK, creatine phosphokinase; CPK-MB, creatine phosphokinase-fraction MB; CT, computed tomography, ECG, electrocardiogram; ECOG, Eastern Cooperative Oncology Group; LDH, lactate dehydrogenase; LVEF, left ventricular ejection fraction; MRI, magnetic resonance imaging; NCI-CTCAE, National Cancer Institute Common Terminology

	ASSESSMENT	TIME
Criteria for Adverse Events; PD, progressive disease; PK, pharmacokinetics, PS, performance status; RECIST, Response Evaluation Criteria In Solid Tumors; WBC, white blood cells.		

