
Criteria for continuation of treatment and for re-treatment
	
In order to be re-treated on Day 1 of a new cycle, the patients will have to fulfill the same criteria as at study entry.
 
If these criteria are not met on Day 1 of a new cycle, treatment administration should be delayed up to two weeks and reevaluated weekly. The new cycle will start upon recovery of these parameters, according to these same criteria.
 
A maximum delay of two weeks is allowed for recovery from drug-related AEs. If toxicities have not recovered after a maximum delay of two weeks, the patient should discontinue the treatment. In the event of obvious clinical benefit, the patient will remain on treatment only after having discussed and agreed upon the case with the Sponsor, and upon recovery of all parameters according to the aforementioned criteria.
 
In order to be re-treated on Day 8 and Day 15 of each cycle, the patients will have to fulfill the following criteria:
 
 a) Platelet count $\geq 75 \times 10^9/l$, hemoglobin ≥ 9 g/dl and ANC $\geq 1.0 \times 10^9/l$. b) ALT and AST $\leq 2.5 \times$ ULN ($\leq 5 \times$ ULN in case of hepatic metastases). c) Other non-hematological toxicities, including renal function, \leq grade 1 (\leq grade 2 in case of asthenia). 
If these criteria are not met on Day 8 or Day 15, the respective infusion will be skipped. If both Day 8 and Day 15 infusions cannot be administered for any reason, the patient should discontinue the treatment, except in the event of obvious clinical benefit, in which case the patient will be allowed to remain on treatment only after having discussed and agreed upon the case with the Sponsor, and upon subsequent recovery of all parameters according to the aforementioned criteria.

Dose reduction
	
Dose reductions will take place based on the worst drug-related toxicity found since the last dose administration.
 
No more than two dose reductions per patient (from 2 mg/m^2 to 1.6 mg/m^2 and then to 1.3 mg/m^2) will be allowed during the study. Patients requiring more than two dose reductions should discontinue the treatment, except in the event of obvious clinical benefit, in which case the patient could be allowed to remain on treatment after having discussed and agreed upon the case with the Sponsor.
 
No dose escalations will be allowed in this study.

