
PLANNED TRIAL PERIODS
	
The total duration of the study will be approximately 33 months, including approximately 24 months of active enrolment.
 
Consenting patients will be followed until death, or until the date of study termination, whichever occurs first.
 
 • Planned start date (first patient on study): 3Q09. • Planned enrolment period: 24 months. • Planned study termination (clinical cutoff): six months after the last treatment visit of the last evaluable patient included in the study or nine months after the last patient is included, whichever occurs first.

SCHEDULE OF ASSESSMENTS AND PROCEDURES

	Screening	Treatment (cycle 1 and further cycles)					Follow-up (1)
Study day	D-28 to D1	D1	D8 D15	D22	D28 (=D1 of the next cycle)	End of treatment (last dose + 30 days)	
Study visit window			Within 2 days of pre-specified day				
Written informed consent	Before any study procedure						
Medical history	•						
Complete physical examination	•	•	Repeat if clinically indicated			•	• (9)
ECOG PS	•	•	Repeat if clinically indicated			•	• (9)
Vital signs	•	•	•		•	•	• (9)
Weight and height	•	Repeat if clinically indicated			•	Repeat if clinically indicated	
Hematology	• (2)	• (2)	• (7)	• (7)	• (7)	•	•
Biochemistry A	• (2)	• (2)	• (7)	• (7)	• (7)	•	•
Biochemistry B	• (2)	Repeat if clinically indicated			• (7)	•	•
Calculated creatinine clearance	• (2)	Repeat if clinically indicated			•	Repeat if clinically indicated	
Pregnancy test	• (3)	Repeat if clinically indicated					
ECG	• (10)	Repeat if clinically indicated			•	•	•
LVEF (cardiac ultrasound)	• (10)	Repeat if clinically indicated			• (8)	•	•
Intercurrent events, concomitant disease and treatments	•	Throughout the “on treatment” period					• (1,9)
Adverse events	NA	Throughout the “on treatment” period					• (1)
Tumor assessment	• (4)	Every other cycle (± 1 week) until PD				•	• (9)
Other tests	•	When indicated, according to the clinical and laboratory context					• (9)
Pharmacokinetics		• (5)	• (5)				
PGx substudy, if patient consented		• (6)					

1. Patients withdrawn with PM00104-related ongoing AEs should be followed with the appropriate tests until their resolution. Beyond 30 days after the last administration of study drug, only those procedures that are relevant to any remaining toxicities need to be performed.

-

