2. Within one week prior to the first administration of PM00104. Repeat on Day 1 of Cycle 1 prior to treatment with PM00104, if the treatment is administered more than one week after the screening test.

Hematology: differential WBC (neutrophils, lymphocytes), hemoglobin and platelets.

Biochemistry A: liver function test (ALT, AP, AST, LDH, total and direct bilirubin), creatinine, CPK, troponin I, glucose and serum electrolytes (Na⁺, Cl⁻, K⁺, Ca⁺⁺, Mg⁺⁺).

Biochemistry B: total protein, albumin, amylase and lipase. CPK-MB fraction to be analyzed if CPK and/or troponin I are abnormal. In the case of grade ≥ 3 increase in serum cardiac troponin I, an ECG and cardiac ultrasound will be performed as soon as possible.

3. Pregnancy test, if applicable, within two weeks prior to registration
4. CT-scan or MRI of all measurable/evaluable sites of disease, as per RECIST. Within four weeks prior to the first dose of PM00104. Documentation of PD is mandatory.
5. First two infusions of the first cycle only.
6. Tissue block collection. Additionally, one blood sample will be taken prior to the first infusion of PM00104.
7. To be performed within the two prior days. If NCI-CTCAE grade ≥ 3 occurs, the appropriate chemistry test(s) should be done at least every 2-3 days until recovery.
8. To be performed every other cycle.
9. After discontinuation, patients taken off study without PD should be monitored every three months until PD, death, other antitumor therapy or the predefined date for study termination. After PD, patients should be monitored every three months until death or the predefined date for study termination.
10. All ECGs and LVEFs (ultrasound) will be reviewed by an external cardiologist.

AE, adverse event; ALT, alanine aminotransferase; AP, alkaline phosphatase; AST, aspartate aminotransferase; CPK, creatine phosphokinase; CPK-MB, creatine phosphokinase-fraction MB; CT, computed tomography; ECG, electrocardiogram; ECOG, Eastern Cooperative Oncology Group Performance Status; LDH, lactate dehydrogenase; LVEF, left ventricular ejection fraction; MRI, magnetic resonance imaging; NA, not applicable; NCI-CTCAE, National Cancer Institute Common Terminology Criteria for Adverse Events; PD, progressive disease; RECIST, Response Evaluation Criteria In Solid Tumors; WBC, white blood cells.

LIST OF ABBREVIATIONS AND DEFINITION OF TERMS

ΔT/ΔC	% Ratio of Treated versus Control Tumor Volumes
AE(s)	Adverse Event(s)
ALT	Alanine Aminotransferase

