PM104-A-004-05§ (1-hour Day 1, 8 and 15 q4wk)	2 (Europe)	49	2.0	1.5	
 Dose level 7 (2 mg/m², RD): grade 4 lipase increase. Dose level 8 and 9 (2.5 and 3.0 mg/m², MTD): grade 3/4 asthenia, grade 3 nausea, grade 1 neutropenia and thrombocytopenia leading to two missing infusions, grade 3 febrile neutropenia, grade 3 anemia, grade 4 neutropenia, grade 4 thrombocytopenia and grade 4 leukopenia. 	Closed (65)

* Additionally, grade 4 troponin I increase without cardiac symptoms or ECG alterations was also reported (no DLT).

**The highest dose level reached up to December 2008 was 3.5 mg/m² (three patients enrolled).

***Recommended dose not achieved; dose intensity is expected to be 1.3 mg/m²/week.

****Prematurely closed due to low recruitment and unpractical dosing schedule.

†The highest dose level reached was 0.475 mg/m²/day.

§This schedule is the same than that used in the current phase II study: PM104-B-001-09.

In all studies, escalating dose cohorts are 1 to 3-6 patients per dose level. DLT, dose-limiting toxicities; ECG, electrocardiogram; MTD, maximum tolerated dose; RD, recommended dose; q3wk, every 3 weeks; q4wk, every 4 weeks

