1.3.5.1. Clinical Safety Data

One hundred and forty patients have been included in phase I trials with PM00104 as of December 2008. Safety data collected from these patients registered in these four phase I clinical trials show gastrointestinal and general disorders (nausea, asthenia, vomiting, anorexia, injection site reactions and diarrhea) as the most frequent PM00104-related adverse events (AEs). Most of these AEs were mild to moderate (i.e., grade ≤2) and recovered without sequelae. Prophylactic antiemetic therapy with dexamethasone plus metoclopramide before the infusions was mandatory, after the emetic events and the DLT observed in the clinical trial PM104-A-001-04 ([Table 6](#)).

With respect to hematological events, decrease in blood cell counts have been observed (a toxicity expected according to preclinical toxicology results), especially at the highest dose levels. In most cases, these hematological events were mild to moderate, transient and not associated with clinical manifestations, such as fever, infection or hemorrhages.

With respect to biochemical events, severe increases in liver transaminases were rare and no grade 4 cases were reported. The laboratory abnormalities usually recovered within few days and no concomitant symptoms were reported.

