As previously mentioned, closer cardiac monitoring was included in the clinical phase I program as a measure of precaution due to some findings in preclinical studies. Cardiac-related disorders found in these phase I studies have consisted of elevations of cardiac troponin I without other symptoms or relevant electrocardiogram (ECG)/echocardiography (ECHO) alterations. Four patients treated in the study PM104-A-004-05 (1-hour Day 1, 8 and 15 q4wk) had grade 4 troponin I increase at the highest dose levels: 2.0 mg/m² (n=2), 2.5 mg/m² (n=1) and 3.0 mg/m² (n=1). None of them had cardiac AEs, abnormal ECG or decrease in left ventricular ejection fraction (LVEF) at the same time than troponin I increase, except one patient treated with 3.0 mg/m² who had grade 1 sinus tachycardia and a slight shortening of the QT interval in the ECG, which recovered by the next cycle. These events were considered not relevant by the investigators and by an external cardiologist who evaluated these cases. ECGs performed as per study protocols before and after each infusion of PM00104 have been reviewed by an external cardiologist and no evidence of cardiotoxicity has been reported. However, close clinical and investigational monitoring of cardiac safety will be continued in subsequent studies with PM00104.

No toxic deaths have occurred in the phase I studies with PM00104.

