1.3.5.2. Results of PM104-A-004-05 trial

This phase I study evaluated the PM00104 schedule (d1, d8 and d15; q4wk) to be used in the current phase II clinical trial (PM104-B-001-09). As of December 2008, 49 patients with malignant solid tumors have been enrolled and treated at the participating institutions (Institut Gustave Roussy, Paris, France and Newcastle General Hospital-Northern Centre for Cancer, Newcastle, United Kingdom). The starting dose was 0.075 mg/m². The dose escalation was increasing at a 100% rate from levels 1 to 4, and at 50% thereafter. No DLTs were documented until dose level 9 (3.0 mg/m²), in which two DLTs were reported. Upon agreement with the investigators, an intermediate dose between this level and the next lowest (2.0 mg/m²) was proposed and subsequent patients were enrolled and treated with a dose of 2.5 mg/m². Three out of eight patients treated with this dose had DLT; therefore, this level and the previously tested next highest were considered maximum tolerated dose (MTD) and the dose of 2.0 mg/m² was defined as the recommended dose (RD). See detail of DLTs in [Table 6](#).

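### No lipase test is scheduled for the Day 8 and Day 15 dosing decisions, although Table 6 lists a grade 4 lipase rise as the only DLT at this dose and schedule

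*Protocol*

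**What the plan says.** **Phase I signal.** Protocol Table 6 (Section 1.3.5) covers the phase I study with the same Day 1, 8 and 15 schedule. Its only entry at dose level 7 (2 mg/m², the recommended dose and the starting dose here) is "grade 4 lipase increase". Section 1.3.5.2, describing the same study, says "No DLTs were documented until dose level 9" (3.0 mg/m²), then refers the reader to Table 6 for the details. The two are not reconciled.

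**When lipase is measured.** Table 9 defines "Biochemistry B: total protein, albumin, amylase and lipase" and fixes that panel on Day 1 of each cycle, with further tests on clinical indication. Hematology and Biochemistry A are weekly. The schedule of assessments agrees: Biochemistry B is conditional on the Day 1, 8, 15 and 22 visits and fixed again only at the start of the next cycle. A repeat every 2 to 3 days is required once a grade 3 or higher value is known.

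**Which rules reach lipase.** The synopsis sets a Day 8/15 limit of grade 1 for "Other non-hematological toxicities, including renal function" (grade 2 for asthenia). Table 11 applies the same limit to related events and exempts only alopecia and vomiting without optimal prophylaxis. If the limit is exceeded, the infusion is skipped. Section 7.2.3.2 requires a dose reduction after a drug-related non-hematological event of grade 3 or 4, and its exclusions do not include lipase. Section 7.2.3 bases reductions on the worst toxicity since the previous dose, so the look-back runs between weekly infusions.

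**The concern.** The weekly panels supply the counts, liver tests and creatinine that Table 11 names. They do not supply the one analyte that Table 6 records as dose-limiting at this dose. A first rise without symptoms gives no clinical reason to test, and the 2 to 3 day repeat cannot start until a high value has already been found. The Day 8/15 limit and the reduction rule would then be applied to lipase without a current value.

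Two things are at stake. A patient with an ongoing drug-related rise could be dosed when the plan says to skip or reduce. And the worst lipase grade per cycle, which SAP 7.5 and 12.3.3 would tabulate, could be understated.

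The plan already treats a comparable signal differently. Section 1.3.5.1 reports that four patients on this schedule "had grade 4 troponin I increase at the highest dose levels", two of them at 2.0 mg/m². Troponin I is in the weekly panel.

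**Working it through.** The plan states no figure on this point. The check sets the schedule beside the dosing rules and counts.

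**Coverage per cycle**
- Infusions: Days 1, 8 and 15 = 3 (Section 7.2.1).
- Fixed lipase values on or just before an infusion: Day 1 only = 1 (Table 9).
- Infusions without a scheduled value: 3 − 1 = 2 of 3.

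**Age of the latest scheduled value**

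| Source | At Day 8 | At Day 15 |
|---|---|---|
| Table 9, sample on Day 1 | 8 − 1 = 7 days | 15 − 1 = 14 days |
| Later cycles, sample two days early | 7 + 2 = 9 days | 14 + 2 = 16 days |
| Cycle 1, screening sample up to 7 days before Day 1 | up to 7 + 7 = 14 days | up to 14 + 7 = 21 days |

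The second row uses schedule note 7: "To be performed within the two prior days". The third row uses the schedule of assessments with its note 2, and Table 8, which let a screening sample from the previous week stand and make a Cycle 1 Day 1 repeat conditional. Table 9 asks for Day 1 of every cycle. The protocol is therefore not uniform for Cycle 1, and the range is shown for that reason.

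**After the Day 15 infusion.** The next fixed sample is the next Day 1. The schedule table labels it Day 28, and a four-week cycle makes it Day 29. Allowing for a sample two days early, the gap is 28 − 15 − 2 = 11 to 29 − 15 = 14 days.

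**With lipase in the weekly panel.** Biochemistry A is drawn at Days 8, 15 and 22 as well as at the start of each cycle. Coverage becomes 3 of 3 infusions, with a value normally 0 to 2 days old at Days 8 and 15, plus a Day 22 value.

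**Which rises the change would reveal.** A weekly pre-dose sample falls 7 − 2 = 5 to 7 days after the previous infusion.
- A rise still present then would be seen. If drug-related and grade 2 or higher, it means a skipped infusion. If grade 3 or 4, it also means a lower dose.
- A rise that came and went within a few days could be missed by weekly tests as well. It would not alter the Day 8/15 re-treatment decision, because the limit would be met on the day.

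**The case against.** The strongest reply is that the clinical evidence is thin. Section 1.3.5.2 contradicts the lipase DLT. Section 1.3.5.1 does not name lipase among the frequent related events, and says of biochemical events: "The laboratory abnormalities usually recovered within few days and no concomitant symptoms were reported". That paragraph names only transaminases, but if lipase behaves the same way, weekly sampling could miss the rise too and the consequence may be small. The text preceding Figure 8 reports a low rate of skipped doses for toxicity at this dose. Lipase is not a named item in the early stopping rule of Section 10.1. It is tested at screening, at the start of each cycle and at end of treatment. SAP 12.3.3 covers it through its footnote on all gradable metabolic parameters, so its absence by name there is not a gap.

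Much of this stands, and it limits the priority. It does not remove the mismatch: two written rules apply to lipase on days when no value is scheduled. A low rate of skipped doses is also weak reassurance, because the available text does not say how often lipase was tested in phase I.

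Three stronger readings should be resisted.
- **That lipase is an established DLT at 2 mg/m².** The documents conflict, and they give no incidence, onset or duration. Section 1.3 refers to the Investigator's Brochure for full details, so the sponsor may hold them.
- **That weekly testing would catch every rise.** It would not, as shown in the working.
- **That the number of decisions measures harm.** Two uncovered decisions for each of 62 evaluable patients gives 124 in Cycle 1. That is not a ceiling, because replaced patients are dosed as well (Section 5.3). It is not a count of lipase events either.

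**Conclusion.** The point holds as a gap between the schedule and the dosing rules. Two of three infusions per cycle have no scheduled lipase value, and the latest one is about 7 days old at Day 8 and about 14 at Day 15 (up to 14 and 21 in Cycle 1 under Table 8). An asymptomatic drug-related rise above grade 1 that persists to Day 8 or Day 15 would go unseen, and the patient would be dosed contrary to the plan.

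This rests on two assumptions: that such persistent rises occur, and that the investigator judges them drug-related adverse events, which Sections 9.1.1 and 9.2.1 leave partly to judgment and to the CRF guidelines. The number of events affected cannot be computed from the documents. A reader might infer that the primary result is compromised. Nothing supports that, because the response-rate analysis does not use lipase. This is a cheap safety improvement of modest priority.

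**What to change.** Move lipase from Biochemistry B to the weekly Biochemistry A panel in the notes to the schedule of assessments and in Tables 8 and 9. Amylase could move with it, but the documents cite no signal for it, so that is optional. No dose, re-treatment or stopping rule needs rewording.

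The cost is one more analyte (two with amylase) on blood already drawn, with no new visit or venepuncture. There is a second, unknown but probably small cost: some infusions would be skipped for rises now unseen. Missing both Day 8 and Day 15 generally means stopping treatment (Section 7.2.2), and fewer than four of the first six infusions can cost efficacy evaluability (Section 8.1). The change could therefore occasionally affect continuation or the evaluable set, though only by applying rules already written.
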